8.5.1 Reporting of Serious Adverse Events

Serious adverse events (SAEs) that are either life-threatening or which result in death must be reported by the PI to the IRB and the Medical Monitor via telephone, fax or email within one business day of discovery. The full report must be submitted to the IRB within 48 hours of initial notification. The Medical Monitor (or their delegate) will then be contacted by the PI and be informed of the details of the SAE, to determine if it meets the reporting requirement of a serious and unexpected suspected adverse reaction. Investigators are required to submit follow-up reports to the initial report as promptly as is feasible. The PI will submit a report of the SAE to the FDA within 15 calendar days of the event, if the event meets the reporting requirement of a serious and unexpected suspected adverse reaction. In those cases, the PI will also report the event to the DSMB. In all other cases, the PI will submit the report as part of periodic reporting to the DSMB and FDA.

Events that are not life-threatening and do not result in death must reported to the IRB within 7 business days of discovery.

The Medical Monitor will review causality (unrelated, not likely related, possibly related, probably related, definitely related) of the serious adverse event. The Medical Monitor

may request further information if necessary and possibly request changes to the protocol or consent form as a consequence of the adverse event.

Additionally, the PI will be responsible for reporting SAEs to the IRB within the time mandated by this IRB. The PI will inform all investigators of any safety updates or changes.

SAEs occurring after a patient has taken the last dose of investigational product will be collected in the clinical data-collection database for 28 days after the last dose of investigational product, regardless of the investigator's opinion of causation. Thereafter, SAEs are not required to be reported unless the investigator assesses the events were related to either investigational product, or a study procedure, and unexpected.

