1.3.2.2 Clinical Studies in Adults

Safety of Baricitinib in general clinical studies

In clinical studies, baricitinib has been generally safe and well tolerated in single doses ranging from 1 mg to 40 mg and in repeat oral doses ranging from 1 mg to 20 mg. Extended safety of baricitinib from all patients exposed to any baricitinib dose (including non-approved doses) pooled from 9 clinical trials (one completed phase 1, three completed phase 2, four completed phase 3 and data through April 1, 2017, from one ongoing phase 3 long-term extension study).

As of 13 August 2022, a total of 14,233 patients received baricitinib in clinical studies. Baricitinib has been approved for clinical use in adult patients in both the European Union and the United States.

• The most commonly reported treatment-emergent adverse events (TEAEs) in patients with RA are upper respiratory infections, nausea, herpes zimplex, and herpes zoster.

- The most commonly reported TEAEs in patients with COVID-19 are increases of liver enzymes, thrombocytosis, creatine phosphokinase increases, neutropenia, deep vein thrombosis, pulmonary embolism, and urinary tract infection.
- The most common alterations in laboratory values involve neutropenia, platelet elevations, liver enzyme elevations, lipid elevations, and creatine phosphokinase elevations.
- Some patients also had decreases in hemoglobin and white blood cells ([WBCs]; neutrophils and other white cell lines).
- Adverse events of special interest include serious infections (including tuberculosus and opportunistic infections), malignancy, and thrombosis. The most common serious infections were pneumonia, herpes zoster, and urinary tract infections.
- As part of the extended safety analysis, 3 individuals were noted to have a gastrointestinal perforation.
- More information about the known and expected benefits, risks, and reasonably anticipated adverse events (AEs) may be found in the Prescribing Information. Information on AEs expected to be related to the investigational product may be found in Section 6 (Adverse Reactions) of the Prescribing Information.

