- Have or have had a history of lymphoproliferative disease; or signs or symptoms suggestive of possible lymphoproliferative disease, or active primary or recurrent malignant disease; or been in remission from clinically significant malignancy for <5 years.
- Have liver abnormalities consistent with severe, chronic liver disease (Appendix 9).
- Have ECG or echocardiogram results that include an arrhythmia unamenable to standard treatment, severe pulmonary hypertension, severe heart valvular (greater than mild insufficiency or stenosis), or significant left heart failure (per AHA guidelines, an LVEF <50% is considered impaired) or right heart failure (RV function described as qualitatively more than mildly diminished systolic function), that in the consideration of the investigator places them at greater risk for participation in the study; have screening electrocardiogram (ECG) abnormalities that, in the opinion of the investigator, are clinically significant and indicate an unacceptable risk for the patient's participation in the study (for example, Bazett's corrected QT interval >450 msec for males and >470 msec for females); have echocardiogram results that, in the opinion of the investigator, places them at greater risk if included in the study.
- Are unable or unwilling to make themselves available for the duration of the study and/or are unwilling to follow study restrictions/procedures.
- Have received an immunosuppressive biologic agent/monoclonal antibody within 4 half-lives prior to entry, for example, anakinra (4 half-lives=18 hours); etanercept (4 half-lives=18 days); infliximab; or adalimumab (4 half-lives=36 days). Use is not indicated in subjects receiving Natalizumab, Nivolumab, Trastuzumab, Denosumab, and Belimumab. Use of IVIg is permitted.
- Have received or be currently treated with BCG (Intravesical), Cladribine, Dipyrone, Pimecrolimus, and Tacrolimus (Topical).

- Are currently enrolled in, or discontinued within the last 30 days from, a clinical trial involving an investigational product or non-approved use of a drug or device (other than the investigational product used in this study), or concurrently enrolled in any other type of medical research judged not to be scientifically or medically compatible with this study.

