8.4.1 Expected and Unexpected Adverse Events

An unexpected adverse event or reaction is defined as any adverse experience, the specificity or severity of which is not consistent with the risks of information described in the protocol. Expected adverse events are those that are identified in the research protocol as having been previously associated with or having the potential to arise as a consequence of participation in the study or are part of the clinical spectrum of the underlying disorder. Common acute and chronic complications of AGS include but are not limited to:

- Seizures
- Intermittent encephalopathy
- Progressive decline in neurologic function
- Skin rashes (such as chilblains) including panniculitis and secondary infections and amputations
- Large vessel central nervous system vasculitis
- Lupus like renal dysfunction
- Autoimmune hepatitis and elevation of liver enzymes and liver function tests
- Pulmonary hypertension
- Cardiomyopathy
- Myopathy
- Glaucoma
- Gastrointestinal disease with bowel inflammation
- Urinary tract infection
- Hip dislocation or scoliosis

- Chronic lung disease
- Spasticity and dystonia
- Feeding difficulties
- Thrombocytopenia
- Anemia
- Hypothyroidism
- Gastroesophageal reflux

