9.4.2.1.4 Malignancy and Lymphoproliferative disorders

Non-melanoma skin cancers (NMSCs) have been reported in patients treated with baricitinib. Periodic skin examination is recommended for patients who are at increased risk for skin cancer.

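### After 28 days off drug, a drug-related SAE that matches a risk already described in the protocol need not be reported or entered

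*Combined protocol and SAP*

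**What the plan says.** Section 8.5.1 sets two rules for SAEs that occur after treatment ends. For the first four weeks they are "collected in the clinical data-collection database for 28 days after the last dose of investigational product, regardless of the investigator's opinion of causation". From then on, no report is required "unless the investigator assesses the events were related to either investigational product, or a study procedure, and unexpected".

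Section 8.4.1 defines the second condition. An unexpected event is one "the specificity or severity of which is not consistent with the risks of information described in the protocol". The counterpart begins: "Expected adverse events are those that are identified in the research protocol as having been previously associated with", and goes on to take in events that could arise from participation or that belong to the clinical picture of AGS. Section 8.5.2 uses a different reference: a SUSAR is judged against the Prescribing Information.

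The protocol is open about known harms. Section 1.3.2.2 states: "Adverse events of special interest include serious infections (including tuberculosus and opportunistic infections), malignancy, and thrombosis". Section 9.4.2.1.5 describes venous thrombosis, pulmonary embolism and arterial events in the limbs, some fatal, and one fatal pulmonary-vascular thrombosis in a patient with AGS. Section 9.4.2.1.6 covers gastrointestinal perforation. On malignancy, section 9.4.2.1.4 says: "Non-melanoma skin cancers (NMSCs) have been reported in patients treated with baricitinib". It names no other tumour type.

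**The concern.** A filter that requires an event to be both related and unexpected keeps unknown harms and releases known ones. Yet the known harms are those the protocol tells investigators to watch for. If the investigator learns five weeks after the last dose of a pulmonary embolism and attributes it to baricitinib, 8.5.1 creates no duty to report it or put it in the database.

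Two things are at stake. The safety summary in 6.3.5 would understate related events of the kinds already described. And the 8.7 stopping rule, which works on very small counts, could be applied to an incomplete count.

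**Working it through.** This is mainly a comparison of texts. The plan states no figure to reproduce.

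**1. The window.** Appendix 2 puts safety closeout at week 292 and the end of scheduled treatment at week 288: 292 − 288 = 4 weeks = 28 days. The 28 days in 8.5.1 therefore match the schedule. They differ by a couple of days from the one-month and 30-day periods in 8.5, which does not affect this point.

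**2. What the late rule does to a related SAE.**

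| Late SAE, judged related | Described in the protocol? | Duty under 8.5.1 after day 28 |
|---|---|---|
| DVT, pulmonary embolism | Yes, fatal cases included (9.4.2.1.5) | None |
| Non-melanoma skin cancer, if it meets the SAE definition | Yes (9.4.2.1.4) | None |
| Gastrointestinal perforation | Yes (9.4.2.1.6) | None |
| Other malignancy | Only as a one-word category (1.3.2.2) | Unsettled |
| Thrombosis at a site not described | Not specifically | Arguably reportable |
| Serious infection | Yes, broadly (9.4.2.1.1) | None under 8.5.1, but 8.4 and 9.4.2.1.1 have their own rules |

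The first three rows assume that expectedness is judged by 8.4.1. Fatal thrombosis is already described, so severity alone would not make a typical case unexpected.

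**3. Comparison with the rest of section 8.**

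- Elsewhere in 8.5.1, and in 8.6, expectedness sets the speed of reporting to FDA. Unexpected related SAEs go within 15 calendar days (7 under 8.6 if fatal or life-threatening). Under 8.5.1 the others go into periodic reports to the DSMB and FDA. Only the post-28-day sentence uses expectedness to remove the duty.
- Section 8.5 asks for aggregate reports that include both expected and unexpected events.
- Section 8.7 halts the study temporarily for one directly related SAE, and stops it for two such non-fatal SAEs or one attributed death. It tests neither expectedness nor time since the last dose. A fatal related embolism on day 35 would count under 8.7 and need not be reported under 8.5.1.
- Section 8.4.2 allows the rating of definite relationship only if all four criteria hold, one being that the event fits a known pattern of response to the drug. Such an event will usually fit the described risks and so be expected. At the top of the causality scale, the two conditions in 8.5.1 pull against each other.

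**4. Weight of one event.** Section 6.3.5 specifies exact binomial 95% intervals. Take n = 55, the planned maximum.

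- 0/55: lower limit 0; upper limit 1 − 0.025^(1/55) = 6.5%.
- 1/55 = 1.8%: lower limit 1 − 0.975^(1/55) = 0.05%; the upper limit solves (1 − p)^55 + 55p(1 − p)^54 = 0.025, giving 9.7%.

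**The case against.** The best defence is that after closeout the protocol means to keep only the SUSAR duty alive, and that 28 days agrees with its schedule. SAEs are collected throughout treatment, which may last 288 weeks or more, and for four weeks afterwards. Section 8.5.3 follows every SAE until it is resolved or stable. The late rule waives a duty and bars nothing; the investigator may still report, and 8.5.1 separately holds the principal investigator to the IRB's own requirements. The AE period in 8.5 also ends one month after cessation, so the aggregate reports may not have been meant to reach later events. All of this limits the gap. None of it explains why an event judged drug-related and known to the investigator should be left out because it is a recognised risk, and none of it removes the conflict with 8.7.

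A reader might go further and infer that malignancy, thrombosis and serious infection can never be reportable after day 28 because all are expected. The documents do not support that:

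- Section 8.4.1 judges by specificity or severity, not by category. A lymphoma or solid tumour could be called unexpected, since 9.4.2.1.4 names only skin cancers.
- Section 8.5.1 does not say whether the protocol or the Prescribing Information governs, and the latter is not part of these documents.
- Section 8.4 makes all infection-related admissions SAEs, and 9.4.2.1.1 sends infections involving hospitalisation or parenteral treatment to the DSMB and IRB within 24 hours. Neither tests expectedness. Their reach after day 28 is unstated, so this is a conflict to settle and not a proven gap.

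A reader might also set the 28 days against the exclusion of patients who have "been in remission from clinically significant malignancy for <5 years". That is an entry criterion and says nothing about how late a drug-induced tumour appears.

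**Conclusion.** The point holds in limited form. As written, a related SAE that arises more than 28 days after the last dose and matches a risk described in the protocol carries no reporting duty under 8.5.1. This is clear for DVT and pulmonary embolism, serious non-melanoma skin cancer and gastrointestinal perforation, provided 8.4.1 defines expectedness. It is unsettled for other malignancies and for serious infection.

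No fraction of missed events can be calculated, because the documents give neither the latency nor the rate of late events. The consequence is one of small counts: a single death is the full 8.7 trigger, and a single non-fatal event is half of the two that stop the study. The change in interval from 0/55 to 1/55 is modest and the two intervals overlap; 55 is also a ceiling. The figures show only that each related event is a visible part of the safety result at this size. The practical effect depends on the investigator learning of the event and judging it related.

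**What to change.** Amend the post-28-day sentence of 8.5.1 by deleting *and unexpected*. Any SAE that the investigator learns of and judges related to baricitinib or a study procedure is then reported and entered, and expectedness decides only how quickly it is sent. In 6.3.5, add a separate listing of related SAEs with onset more than 28 days after the last dose, so that they are not mixed with events from the fully collected period.

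Reconcile 8.5.1 with 8.4 and 9.4.2.1.1 (whether the infection rules continue after day 28) and with 8.7 (whether late related events enter the stopping count). State whether the protocol or the Prescribing Information defines expectedness, since it would still govern reporting speed.

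The cost is a two-word deletion, a few clarifying sentences, one listing and an occasional extra SAE form. No visit, dose or follow-up contact is added. Ascertainment after day 28 therefore stays passive, and the listing should say so: it would show known late events and would not support a late incidence rate.

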8.5.2 Suspected Unexpected Serious Adverse Reactions

Suspected unexpected serious adverse reactions (SUSARs) are serious events that are not listed in the Prescribing Information and that the investigator identifies as related to investigational product or procedure.

8.5.3 Follow-up report

If an SAE has not resolved at the time of the initial report and new information arises that changes the investigator's assessment of the event, a follow-up report including all relevant new or reassessed information (e.g., concomitant medication, medical history) should be submitted to the IRB. The investigator is responsible for ensuring that all SAE are followed until either resolved or stable.

8.6 Notifications of SAEs/IND Safety Reports to the FDA

Unexpected fatal or life-threatening adverse events that are related to the study drug, will be reported to FDA as soon as possible but no later than 7 calendar days following the sponsor's initial receipt of the information.

Unexpected serious adverse events that are related to the study drug but not fatal or life-threatening, will be reported to FDA as soon as possible but no later than within 15 calendar days following the sponsor's initial receipt of the information.

Follow-up reporting: Any relevant additional information obtained by the sponsor that pertains to a previously submitted IND safety report will be submitted as a Follow-up IND Safety Report. Such report will be submitted as soon as the information is available, but no later than 15 calendar days after the sponsor receives the information.

8.7 Study Stopping Rules

There are some circumstances which potentially may arise, requiring temporary study stop. A serious adverse event, directly related to the use of study drug, will prompt a temporary stop to discuss the event with the DSMB and FDA. The IRB will be notified in accordance with CHOP IRB SOP 408. The study will proceed only with documented concurrence of the DSMB, FDA and the IRB, as applicable.

The occurrence of two non-fatal SAEs directly related to use of the study drug or one death directly attributed to use of the study drug will stop the study.

8.8 Safety Management and Monitoring Guidance

The following Appendices should be followed. Appendices 9-12 in particular serve as guidance for management of abnormal laboratory values identified during screening or safety follow-up of enrolled individuals.

Study schedule, Overall	Appendix 1
Study Timeline	Appendix 2
Dose Escalation Schedule for Patients with eGFR ≥60 mL/min/1.73 m2 or Normal eGFR for Age <24 Months	Appendix 3
Dose Escalation Schedule for Patients with eGFR 30 - <60 mL/min/1.73 m2 or for Age <24 Months with abnormal eGFR	Appendix 4
AGS severity scale	Appendix 5
Patient Daily Diary for AGS infants 0-6 months	Appendix 6
Patient Daily Diary for AGS > 6 months	Appendix 7
Clinical Laboratory Tests	Appendix 8
Management of Liver Enzyme Laboratory Values	Appendix 9
Management of Leukocyte associated laboratory testing and IgG	Appendix 10
Management of Anemia	Appendix 11
Management of Thrombocytopenia and Thrombocytosis	Appendix 12
Cutaneous LE Disease Area and Severity Index (CLASI)	Appendix 13
Dose tapering guidance	Appendix 14
Decision tree in case of infection suspicion or confirmation	Appendix 15
Concomitant medication approach in patients with AGS receiving baricitinib	Appendix 16

9 STUDY ADMINISTRATION

9.1 Treatment Assignment Methods

9.1.1 Randomization

There are no randomization procedures.

9.1.2 Blinding

There are no blinding procedures.

9.1.3 Unblinding

There are no unblinding procedures.

9.2 Data Collection and Management

9.2.1 REDCap for Study Data Management

The study will utilize REDCap to provide a Web-based data collection, data management system. REDCap is an NIH-supported, broadly-used tool developed and continually improved by Vanderbilt University. CHOP has had very substantial experience in the implementation and support of REDCap data bases for clinical trials. Specifically, [name] already has in place a REDCap database designed specifically for AGS. Database fields correspond to expected disease complications and anticipated possible adverse outcomes. CHOP provides support for the management and curating of datasets from REDCap. Especially important are reports to the Data and Safety Monitoring Board (DSMB) charged with ensuring the safety of study participants. Finally, the database is directly accessible to standard statistical packages such as SAS, SPSS, and STATA so that interim and final analyses can be conducted without the need to transport data. REDCap reports will monitor recruitment overall. It will warn of recruitment problems by plotting actual vs. expected screens, recruits and enrollees.

9.2.2 Additional Study Data Management

The study will also utilize OnCore Clinical Trials Management System and Advarra EDC, CHOP Research IS secured electronic data capture systems, which will be used for study scheduling, data collection and analysis (e.g. eCRFs), as well as billing and regulatory purposes. OnCore Clinical Trials Management System and Advarra EDC are secure electronic data capture systems with access controls and a data backup plan. The systems are password protected. Only study team members will have access to study documents, subject data and case report forms stored in these systems. Access to the systems is monitored and logged for review if needed.

9.2.3 Data Security

There are several layers of security that protect the data stored in REDCap and OnCore. The first layer consists of network security, through firewalls, and is designed to limit access to authorized users and to deny access to all others. The firewall blocks malware and prevents flooding. The second layer consists of database authentication. This limits access to the database to those individuals passing layer one who have an assigned database account and can enter the correct, suitably complex, user-defined password for that account. The third layer consists of controlling a user's capabilities, what a user can see and do, based on the user's role in each investigation. Each user needing access to the data for a study must be included on the list of key staff for that specific study in the protocol and must be assigned a study role. If a user is not in the key staff list of the study s/he will not be granted access to that study's data even if s/he has a valid password associated with another study. Key staff will only be allowed to perform those tasks that are dictated by the person's defined role in the study. For instance, a person who enters data will only be able to add records to specific data files; s/he cannot peruse or make changes to existing records in the database. Only those persons who have clinical responsibilities for the patient would be able to see patient identifying information. There is provision for the PI to be able to over-ride, to widen or narrow, the capabilities assigned based on study role.

Lastly, to protect patient confidentiality, study research data is coded and separated from all patient identifying information. The confidential data is stored separately and the information is encrypted to offer additional protection. Each research participant in a study is assigned an anonymous participant ID number that can be used to link together a participant's de-identified research records but not to link directly to the confidential identifying data. Since there must be a way to link to that data to identify patients for scheduling and mailings, etc., a second arbitrary number called a universal identifier is assigned to each participant's confidential data record. That number is linked to the participant ID via a second translation file that is also encrypted. Therefore, in the extremely unlikely event that an unauthorized person gained access to the confidential data file all s/he would see is gibberish without having the appropriate key to decrypt the data. Likewise, all transmissions to and from REDCap are sent using secure HTTP (HTTPS), which encrypts all transmissions so that even if they were intercepted their content would be unreadable by all but the intended recipient.

There are also two other components to security and they are monitoring and system administration. The network is closely monitored and all activity is logged. Both the real time monitor and the logs are reviewed by eye and by computer to identify suspicious activity so that it can be dealt with appropriately. Furthermore, all access to research data is audited and all activities are logged so that if a problem occurs it will be possible to identify who was responsible and how it happened. The system and database software are kept up-to-date with the latest security protections released for the operating system and for the database. These measures help us to keep ahead of the threats to security or to close loopholes before they can be more widely exploited. Finally, there is excellent physical security; access to the systems is key pad controlled, there is a backup generator to provide power to keep systems operating in the event of power failure, all computer rooms housing database and web servers are environmentally-controlled and protected against flood and fire.

